## **8.1 Serious Adverse Event Reporting (SAE)**

An adverse event or suspected adverse reaction is considered “serious” if, in the view of either the investigator or the sponsor, it results in any of the following outcomes:

- Death
- A life-threatening adverse drug experience – any adverse experience that places the patient, in the view of the initial reporter, at immediate risk of death from the adverse experience as it occurred. It does not include an adverse experience that, had it occurred in a more severe form, might have caused death.

- Inpatient hospitalization or prolongation of existing hospitalization.
- A persistent or significant incapacity or substantial disruption of the ability to conduct normal life functions.
- A congenital anomaly/birth defect.

Important medical events that may not result in death, be life-threatening, or require hospitalization may be considered a serious adverse drug experience when, based upon appropriate medical judgment, they may jeopardize the patient or subject and may require medical or surgical intervention to prevent one of the outcomes listed in this definition. Examples of such medical events include allergic bronchospasm requiring intensive treatment in an emergency room or at home, blood dyscrasias or convulsions that do not result in inpatient hospitalization, or the development of drug dependency or drug abuse (21 CFR 312.32).

- Important medical events as defined above, may also be considered serious adverse events. Any important medical event can and should be reported as an SAE if deemed appropriate by the Principal Investigator or the IND Sponsor, IND Office.
- All events occurring during the conduct of a protocol and meeting the definition of a SAE must be reported to the IRB in accordance with the timeframes and procedures outlined in "The University of Texas M. D. Anderson Cancer Center Institutional Review Board Policy for Investigators on Reporting Unanticipated Adverse Events for Drugs and Devices". Unless stated otherwise in the protocol, all SAEs, expected or unexpected, must be reported to the IND Office, regardless of attribution (within 5 working days of knowledge of the event).

Investigator may include protocol specific reporting criteria here if desired.

- All life-threatening or fatal events, that are unexpected, and related to the study drug, must have a written report submitted within 24 hours (next working day) of knowledge of the event to the Safety Project Manager in the IND Office.
- Unless otherwise noted, the electronic SAE application (eSAE) will be utilized for safety reporting to the IND Office and MDACC IRB.
- Serious adverse events will be captured from the time of the first protocol-specific intervention, until 30 days after the last dose of drug, unless the participant withdraws consent. Serious adverse events must be followed until clinical recovery is complete and laboratory tests have returned to baseline, progression of the event has stabilized, or there has been acceptable resolution of the event.
- Additionally, any serious adverse events that occur after the 30 day time period that are related to the study treatment must be reported to the IND Office. This may include the development of a secondary malignancy.

Reporting to FDA:

- Serious adverse events will be forwarded to FDA by the IND Sponsor (Safety Project Manager IND Office) according to 21 CFR 312.32.

It is the responsibility of the PI and the research team to ensure serious adverse events are reported according to the Code of Federal Regulations, Good Clinical Practices, the protocol guidelines, the sponsor's guidelines, and Institutional Review Board policy

Investigator Communication with Supporting Companies:

Serious adverse event reporting requirements to supporting companies can be added here if needed.

**8.2** Important medical events that may not result in death, be life-threatening, or require hospitalization may be considered a serious adverse drug experience when,, based upon appropriate medical judgment, they may jeopardize the patient or subject and may require medical or surgical intervention to prevent one of the outcomes listed in this definition. Examples of such medical events include allergic bronchospasm requiring intensive treatment in an emergency room or at home, blood dyscrasias or convulsions that do not result in inpatient hospitalization, or development of drug dependency or drug abuse (21 CFR 312.32).

- a. Important medical events as defined above, may also be considered serious adverse events. Any important medical event can and should be reported as an SAE if deemed appropriate by the Principal Investigator or the IND Sponsor/the IND office.
- b. All events occurring during the conduct of a protocol and meeting the definition of a SAE must be reported to the IRB in accordance with the timeframes and procedures outlined in "University of Texas M.D. Anderson Cancer Center Institutional Review Board Policy on Reporting Serious Adverse Events". Unless stated otherwise in the protocol, all SAEs, expected or unexpected, must be reported to the IND office regardless of attribution.
- c. All grade 3-5 reactions to the vaccination and all unexpected SAEs will be reported in an expedited fashion.
- d. All life-threatening or fatal events, expected or unexpected, and regardless of attribution to the study drug, must have a written report submitted within 24 hours(next working day) of knowledge of the event to the Safety Project Manager in the IND office.
- e. The MDACC "Internal SAE Report Form for Prompt Reporting" will be used for reporting to the-IND office
- f. Serious adverse events will be captured from the time the patient signs consent until 30 days after the last application of R848. Serious adverse events must be followed until clinical recovery is complete and laboratory tests have returned to baseline, progression of the event has stabilized, or there has been acceptable resolution of the event.
- g. Additionally, any serious adverse events that occur after the 30 day time period that are related to the study treatment must be reported to the IND office. This may include the development of a secondary malignancy.
- h. The adverse events will be recorded in PDMS according to the following guidelines.

8.3.1 Reporting to FDA - Serious adverse events will be forwarded to FDA by the IND Sponsor (Safety Project Manager in the IND office) according to 21 CFR 312.32.

8.4 It is the responsibility of the PI and the research team to ensure serious adverse events are reported according to the Code of Federal Regulations, Good Clinical Practices, the protocol guidelines, and Institutional Review Board policy.

Recommended Adverse Event Recording Guidelines					
Attribution	Grade 1	Grade 2	Grade 3	Grade 4	Grade 5
Unrelated	Phase I	Phase I	Phase I Phase II	Phase I Phase II Phase III	Phase I Phase II Phase III
Unlikely	Phase I	Phase I	Phase I Phase II	Phase I Phase II Phase III	Phase I Phase II Phase III
Possible	Phase I Phase II	Phase I Phase II Phase III			
Probable	Phase I Phase II	Phase I Phase II Phase III			
Definitive	Phase I Phase II	Phase I Phase II Phase III			

Tumor response to therapy this study will be done using immune-related response criteria (irRC) which is a modified version of WHO criteria.

**9.1 Definition of Measureable and Non-Measurable Lesions** Measurable Lesions are lesions that can be accurately measured in two perpendicular diameters, with at least one diameter  $> 10$  mm. The area will be defined as the product of the largest diameter with its perpendicular. Skin lesions can be considered measurable. Cutaneous lesions that are  $> 5$  mm in diameter can be considered measurable.

**Non-Measurable (evaluable) Lesions** are all other lesions, including unidimensionally measurable disease and small lesions.

**9.2 Definition of Index/Non-Index Lesions**

In many patients, all measurable disease will be cutaneous, so we will allow all 10 index lesions to be in a single organ. All measurable lesions, up to a maximum of ten lesions in total, should be identified as *index* lesions to be measured and recorded on the medical record at baseline. The *index* lesions should be representative of all involved organs. In addition, *index* lesions should be selected based on their size (lesions with the longest diameters), their suitability for accurate repeat assessment by imaging techniques, and how representative they are of the patient's tumor burden. A sum of the products of diameters (SPD) for all *index* lesions will be calculated and considered the baseline sum of the products of diameters. Response criteria to be followed are listed below. The baseline sum will be used as the reference point to determine the objective tumor response of the *index* lesions at tumor assessment (TA). Measurable lesions, other than *index* and all sites of non-measurable disease will be identified as *non-index* lesions. *Non-index* lesions will be recorded on the medical record and should be evaluated at the same assessment time points as the *index* lesions. In subsequent assessments, *non-index* lesions will be recorded as "stable or decreased disease," "absent", or "progression."

**9.3 Definition of Tumor Response Using irRC**

The sum of the products of diameters at tumor assessment using the immune-related response criteria (irRC) for progressive disease incorporates the contribution of new measurable lesions. Each net Percentage Change in Tumor Burden per assessment using irRC criteria accounts for the size and growth kinetics of both old and new lesions as they appear.

**Definition of Index Lesions Response Using irRC**

**irComplete Response (irCR):** Complete disappearance of all *index* lesions. This category encompasses exactly the same subjects as "CR" by the mWHO criteria.

**irPartial Response (irPR):** Decrease, relative to baseline, of 50% or greater in the sum of the products of the two largest perpendicular diameters of all *index* and all new measurable lesions (i.e., Percentage Change in Tumor Burden). Note: the appearance of new measurable lesions is factored into the overall

tumor burden, but does not automatically qualify as progressive disease until the SPD increases by  $\geq 25\%$  when compared to SPD at nadir.

**irStable Disease (irSD):** Does not meet criteria for irCR or irPR, in the absence of progressive disease.

**irProgressive Disease (irPD):** At least 25% increase Percentage Change in Tumor Burden (i.e., taking sum of the products of all *index* lesions and any new lesions) when compared to SPD at nadir.

#### **Definition of Non-Index Lesions Response Using irRC**

**irComplete Response (irCR):** Complete disappearance of all *non-index* lesions. This category encompasses exactly the same subjects as "CR" by the mWHO criteria

**irPartial Response (irPR) or irStable Disease (irSD):** *non-index* lesions are not considered in the definition of PR, these terms do not apply.

**irProgressive Disease (irPD):** Increases in number or size of *non-index* lesions does not constitute progressive disease unless/until the Percentage Change in Tumor Burden increases by 25% (i.e., the SPD at nadir of the index lesions increases by the required amount).

#### **Impact of New Lesions on irRC**

New lesions in and by themselves do not qualify as progressive disease. However, their contribution to total tumor burden is included in the SPD which in turn feeds into the irRC criteria for tumor response. Therefore, new non-measurable lesions will not discontinue any subject from the study.

#### **9.4 Definition of Overall Response Using irRC**

Overall response using irRC will be based on these criteria:

**Immune-Related Complete Response (irCR):** Complete disappearance of all tumor lesions (index and non-index together with no new measurable/unmeasurable lesions) for at least 4 weeks from the date of documentation of complete response.

**Immune-Related Partial Response (irPR):** The sum of the products of the two largest perpendicular diameters of all index lesions is measured and captured as the SPD baseline. At each subsequent tumor assessment, the sum of the products of the two largest perpendicular diameters of all index lesions and of new measurable lesions are added together to provide the Immune Response Sum of Product Diameters (irSPD). A decrease, relative to baseline of the irSPD compared to the previous SPD baseline, of 50% or greater is considered an immune Partial Response (irPR).

**Immune-Related Stable Disease (irSD):** irSD is defined as the failure to meet criteria for immune complete response or immune partial response, in the absence of progressive disease.

**Immune-Related Progressive Disease (irPD):** It is recommended in difficult cases to confirm PD by serial imaging. Any of the following will constitute progressive disease:

- At least 25% increase in the sum of the products of all index lesions over baseline SPD calculated for the index lesions.
- At least a 25% increase in the sum of the products of all index lesions and new measurable lesions (irSPD) over the baseline SPD calculated for the index lesions.

#### **Immune-Related Response Criteria Definitions**

Index Lesion Definition	Non-Index Lesion Definition	New Measurable Lesions	New Unmeasurable Lesions	Percent Change in Tumor Burden	Overall irC Response
Complete Response	Complete Response	No	No	-100%	irCR
Partial Response	Any	Any	Any	$\geq -50\%$ $<50\%$ to $<+25\%$ $>+25\%$	irPR irSD irPD
Stable Disease	Any	Any	Any	$<50\%$ to $<+25\%$ $>+25\%$	irSD irPD
Progressive Disease	Any	Any	Any	$\geq +25\%$	irPD

#### **9.5 Immune-Related Best Overall Response Using irRC (irBOR)**

irBOR is the best confirmed irRC overall response over the study as a whole, recorded between the date of first dose until the last tumor assessment before subsequent therapy (except for local palliative radiotherapy for painful bone lesions) for the individual subjects in the study. For assessment of irBOR, all available assessments per subject are considered.

If a lesion is surgically resected or treated with definitive radiosurgery, the size of the lesion prior to the definitive local therapy will be included in the calculated irBOR.

Primary evidence of antineoplastic activity will be evaluated as a function of objective tumor response following the vaccination period. An overall objective assessment of all measurable and non-measurable disease will be performed as outlined in 9.1. Tumor assessments should be performed by physical exam, ultrasound, MRI or CT scan, throughout the study. The treating physicians will perform tumor measurement.

Radiological studies must account for all lesions that were present at baseline and must use the same techniques as used at baseline. All

complete and partial responses must be confirmed by a second assessment at least four weeks later.

#### **9.6 Baseline measurement**

In this trial a period of immunization opens the treatment, and immunization alone mediates tumor response rarely. (Cancer immunotherapy: moving beyond current vaccines. Rosenberg SA, Yang JC, Restifo NP. *Nat Med.* 2004 Sep;10(9):909-15.) So with this sequence, as has been seen with other immunologic mediators, we should expect that a period of progression may precede any response from the treatment.

Therefore, because subjects are likely to progress during the vaccination portion of the study, the baseline will be that measurement during the first 10 weeks of the study at which the tumors are at their maximum size (based on sum of LD). Progression will be allowed during these first 10 weeks without withdrawal of the subject from treatment or from the study. This includes increase in the size of the lesions as well as the appearance of new lesions.

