Blood samples will be obtained serially in order to determine the immune response against the gp100(g209-2M) and MAGE-3 vaccines (weeks 0, 2, 4, 8, 12, 16, 20, and 24: weeks 8 and 16 will not be collected when leukapheresis is performed; blood samples will be collected by leukapheresis at weeks 0 and 8 (+/- 1 week), and 16 when feasible). To evaluate the inflammatory infiltrate at the site of immunization, biopsies will be obtained of vaccination sites as outlined in section 7.3

Subjects in the adjuvant cohort.

Vaccination will continue for the designated 8 weeks. Blood draw and pheresis times will be the same as subjects in the metastatic disease cohorts. Subjects will be monitored for disease recurrence, but if recurrence occurs prior to the completion of blood draws or pheresis these tests can still be obtained if deemed valid by the PI.

Subjects in the metastatic disease cohort:

At the end of 8 weeks, we will allow tumor progression since patients will have only received vaccine at this point. We estimate that of a total of approximately 24 patients in this cohort, 17% will drop off at this point, leaving a total of 20 patients to be treated in Part 2. To have enough patients to evaluate the secondary endpoints, 20 additional patients may be enrolled in the metastatic disease cohort so that at least 30 patients (10/arm) with gel and 10 are available for Part 2.

At the end of 8 weeks of vaccine, cutaneous lesions (at least 2 and up to 10 lesions) will be assigned by the physician according to region to receive or not to receive 0.2% R848 gel. The CORe randomization system will not be used in Part 2. The physician will designate the regions and which tumors will be treated. The area of cutaneous lesions will be divided into two regions, Region A and Region B, striving to equalize tumor burden in each designated region as best as possible. When feasible, Region A will be a proximal group of lesions, and B distal. When this proximal – distal differentiation is not feasible because of the characteristics of the metastatic pattern, then A and B will be assigned to regions in no particular order. If the two regions coalesce during the vaccination phase, the coalesced tumor may be divided into two regions. Each target tumor whether it is treated or untreated will be marked, measured and photographed for the medical record. Because this dose provides the highest level of immune cell

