**Vaccine biopsies:** Vaccine sites will be biopsied from all patients in the study when feasible. The vaccine site biopsied will be a GP100 vaccine site. The vaccine site will be identified and a punch biopsy taken of full thickness skin with standard sterile technique and closure. Vaccine sites will be biopsied at 24 hrs (+/- 6 hours) after the first gp100(g209-2M) vaccine and at week two of vaccination. These biopsies will occur the day following the vaccination for that week. Failure to obtain vaccine biopsies due to refusal, discretion of the investigators or infeasibility will not constitute a violation of the trial.

**Tumor biopsies** will be taken from patients in the cohort with metastatic disease. There will be no tumor biopsies in patients enrolled in the adjuvant cohort. The first

biopsy will be taken as a base line at any time after enrollment onto the trial, but prior to the first vaccination. A second tumor biopsy will be taken at week 8 prior to the first dose of R848 on the tumors, and at week 12 (4 weeks after initiating R848 therapy on the tumors, but at any time during that week) Tumors will be randomly selected when biopsied, but when feasible, a biopsy will be taken of both a treated lesion and untreated lesion at week 12. Tumor biopsies may be taken using any biopsy method to optimize tumor yield using standard sterile techniques. Tumor volume may not allow for all biopsies to be obtained in all individuals, in this case pre-vaccine biopsies and week 12 will take precedence. Tumor biopsies are at the option of the enrolled subject and the investigators, and failure to obtain tumor biopsies due to refusal, inadequate remaining tumor volume, discretion of the investigators or infeasibility will not constitute a violation of the trial.

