### 8.0 Serious Adverse Event Reporting (SAE)

Vaccines are usually well-tolerated. They may cause discomfort, swelling, and/or redness around the injection site. While there has not been significant autoimmune symptoms caused by gp100(g209-2M) or MAGE-3 peptide vaccines alone, patients who experience any Grade III or greater autoimmune reactivity, except for local skin reactions, will be taken off the study. The occurrence of 3 patients with Grade III or greater toxicity will stop the entry of the study until an assessment of the risks, coordination with MD Anderson IRB and appropriate modifications of the informed consent can be completed.

The most frequent systemic toxicities associated with Resiquimod are fever, fatigue, headache, pain, dizziness, myalgia, chills, and a small increase in absolute lymphocyte count. Localized toxicities reported are erythema, edema, ulceration, weeping, scabbing, flaking, pruritis, and numbness/tingling. Other infrequent toxicities reported that may be related are abnormal LFT, abdominal cramping, nausea, vomiting, diarrhea, backache, neck pain, rhinitis, and urticaria.

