### **10.0 Criteria for Removal From The Study**

#### **10.1 Disease progression:**

All patients who develop recurrent disease will be taken off the study. Patients in the either cohort may complete their laboratory evaluation (blood draws, biopsies and pharesis) if they recur/progress before week 16. Patients will be allowed to continue on the study if their disease progresses during the first 10 weeks of study, since they will have only received vaccine +/- local TLR agonist at this point. For subsequent evaluations, patients with progressive disease will be removed from the treatment.

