## 11.0 Statistical Considerations

### Overview

This is a randomized phase II trial enrolling melanoma patients who are HLA-A2+ with or without HLA-DP4+. Patients of two separate types will be enrolled in separate cohorts. One cohort includes patients who are NED but at high risk for recurrence. The second cohort will include patients with non-visceral metastatic disease and must have at least two evaluable and biopsiable lesions to be eligible for the trial.

The trial will have two parts. In Part 1 (both cohorts), we will fairly randomize patients to receive either the gp100(g209-2M) +/-MAGE3 peptide vaccine plus a topical TLR 7 /8 agonist, R848, (Arm A) or the gp100(g209-2M) +/- MAGE3 vaccine alone Arm B). The randomization will be stratified by cohort. A total of 48 patients will be enrolled, 24 per arm. All patients will receive the gp100(g209-2M) vaccine (those who are HLA-DP4 + will also receive the MAGE3 vaccine) weekly (for 8 weeks) and the patients randomized to receive R848 gel will have the gel applied to the gp100(g209-2M) vaccine site weekly.

After 8 weeks of treatment on Part 1, Part 2 of the trial begins. In Part 2 (only patients in the metastatic disease cohort), the treating physician will divide the area of cutaneous lesions into regions, Region A and Region B and designate the two regions to receive or not to receive R848. At least one lesion will be randomly assigned to receive R848 from weeks 8 through 24, and one will not. One lesion from each region will be chosen for biopsy as outlined in section 7.3. If a patient has more than two evaluable lesions, we will stratify by lesion size to assure that the lesions will be comparable.

As a safety measure, if a patient's untreated lesions grow while treated lesions are stable or shrink, all lesions will be treated with R848. This will occur after the assessment of the primary endpoints of the study, so it will not affect the analysis of these endpoints.

In April 2015, the trial is being further modified to add an additional 20 patients with metastatic disease, all of whom will receive the the gp100(g209-2M) +/-MAGE3 peptide vaccine plus R848 (Arm C). These patients will not be part of the primary comparative study analysis of T-cell responses in the blood. The purpose of these patients is to provide additional information on characterizing tumor response, defined as at least a 50% shrinkage in tumor size by irRC criteria.

### Part 1

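### The irRC baseline may be taken up to week 10, but R848 goes onto the tumours at week 8, so an on-treatment reading can become the reference for response

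*Combined protocol and SAP*

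**What the plan says.** Section 9.6 defines the response baseline: "the baseline will be that measurement during the first 10 weeks of the study at which the tumors are at their maximum size". The time point is selected on the sum of longest diameters. The stated reason is that an allowance is needed "because subjects are likely to progress during the vaccination portion of the study".

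Several sections place the start of tumour gel at week 8. The section 11.0 Overview says "At least one lesion will be randomly assigned to receive R848 from weeks 8 through 24, and one will not". Section 7.3 says "A second tumor biopsy will be taken at week 8 prior to the first dose of R848 on the tumors", and describes week 12 as "4 weeks after initiating R848 therapy on the tumors". Section 6.0 has the gel applied twice weekly, in clinic for the first two weeks.

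Section 8.0 lists the local effects of the gel: "Localized toxicities reported are erythema, edema, ulceration, weeping, scabbing, flaking, pruritis, and numbness/tingling".

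Under section 9.4, irPR is a fall of at least 50% in the sum of products of diameters (SPD, including new measurable lesions) from baseline. Two analyses depend on it:

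- the one-sided exact binomial test in Arms A and C (30 patients, 5% against 22%);
- the within-patient McNemar comparison of gel-treated and untreated lesions.

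The progression allowance appears with two limits. Section 6.0 says "At the end of 8 weeks, we will allow tumor progression since patients will have only received vaccine at this point". Section 10.1 says "Patients will be allowed to continue on the study if their disease progresses during the first 10 weeks of study", and section 9.6 also uses 10 weeks.

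**The concern.** The window for choosing the baseline runs two weeks past the period that justifies it, and those weeks are on tumour gel. Nothing in the plan restricts the baseline to readings taken before the gel. Because the rule takes the maximum, a larger post-gel reading, if one exists, has to be used.

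Two things can make such a reading larger. One is gel-induced swelling, which affects only the lesions that receive gel. The other is true growth in the first two weeks of gel, which can affect any lesion. Either one raises the reference, so a fall of 50% from it is less than a 50% fall from the pre-gel size. The binomial test compares the resulting rate with a 5% standard-of-care rate, so a softer definition of response matters there. In the McNemar comparison the swelling part is one-sided, because untreated lesions cannot swell from gel that they do not receive.

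**Working it through.** **1. How a post-gel reading could arise.** Section 11.0 schedules response assessment at weeks 8, 16 and every 8 weeks after that. Section 7.1 puts visits after week 4 at 4-week intervals with a window of 1 week either way, and the week-8 CT has the same window. The scheduled points nearest the interval are therefore weeks 8 and 12, with none strictly between gel start and week 10. The possible sources are:

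- a week-8 visit or scan done late, up to week 9, after gel has begun;
- an unscheduled measurement, for example around the clinic gel applications in weeks 8 to 10.

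**2. The plan's own figure.** For 30 patients, the smallest rejection count with one-sided exact alpha at or below 5% against a 5% rate is 5. At least 4/30 gives alpha 6.08%; at least 5/30 gives 1.56%. Power at 22% is 82.1%, which reproduces the stated 82%.

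**3. Effect of a swollen baseline.** Swelling sizes are assumptions. Let both diameters of the treated lesions rise by a proportion s, so their SPD is multiplied by m = (1 + s)².

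- Treated region alone: return to pre-gel size reads as 1/m − 1. The true shrinkage needed for irPR is 1 − 0.5m.
- Patient level, half the burden treated and the untreated half unchanged: baseline is 0.5m + 0.5, and return to pre-gel size reads as 1/(0.5m + 0.5) − 1. Total SPD must fall to 0.25m + 0.25, which leaves 0.25m − 0.25 for the treated half. The treated-region shrinkage needed is 1 − (0.25m − 0.25)/0.5 = 1.5 − 0.5m.

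| s | m | Region: resolution reads | Region: shrinkage needed | Patient: baseline | Patient: resolution reads | Patient: treated-region shrinkage needed |
|---|---|---|---|---|---|---|
| 0 | 1.00 | 0% | 50% | 1.00 | 0% | 100% |
| 10% | 1.21 | −17% | 39.5% | 1.105 | −10% | 89.5% |
| 20% | 1.44 | −31% | 28% | 1.22 | −18% | 78% |
| 30% | 1.69 | −41% | 15.5% | 1.345 | −26% | 65.5% |
| 41% | 2.00 | −50% | 0% | 1.50 | −33% | 50% |
| 73% | 3.00 | −67% | 0% | 2.00 | −50% | 0% |

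Resolution of swelling alone therefore scores irPR at about +41% diameter for the treated region, and at about +73% at patient level.

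**4. Sensitivity of the binomial test.** Suppose a share f of true non-responders is scored as responders. The rate under the null becomes p = 0.05 + 0.95f. The chance of at least 5/30 is then:

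| f | p | P(at least 5/30) |
|---|---|---|
| 0 | 0.050 | 0.0156 |
| 2% | 0.069 | 0.0525 |
| 3% | 0.0785 | 0.082 |
| 5% | 0.0975 | 0.163 |

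The documents do not allow f to be estimated. The table shows only that a 30-patient test against 5% has little slack.

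**The case against.** **Exposure is limited.** No tumour assessment is scheduled between gel start and week 10. The research nurse applies the gel, whereas section 9.5 gives measurement to the treating physicians. Section 6.0 has the target lesions marked, measured and photographed when regions are assigned, so a pre-gel reading should normally exist. This stands. A reader might infer that a swollen reading will routinely become the baseline; the schedule does not support that.

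**Ten weeks may be deliberate.** Section 9.6 also expects progression to precede response. In addition, weekly dosing with 2 days' slack over 7 intervals could add 14 days, so vaccination could end at week 10. Both are fair readings. The first is a reason to tolerate early growth, not to use a post-treatment maximum as the denominator of response. The second is met by tying the baseline to the first tumour application, which moves with any delay.

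**Swelling may persist.** Gel continues to week 24 and can go on for up to 4 months more, and a response needs confirmation at least 4 weeks later. If oedema is still present at assessment, no false response appears, and a pre-gel baseline would count against treated lesions. This stands as a limit on the size of the effect. It does not remove the problem, because section 9.5 takes the best confirmed response over all available assessments, and confirmation shows only that the smaller size lasted. A sensitivity analysis covers both possibilities.

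**The numbers are assumed.** Section 8.0 names edema without a size and does not say that lesion diameters increase. That is correct, and is why a range is shown.

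**Conclusion.** The point holds in a limited form. As written, section 9.6 lets a measurement made after tumour gel has started serve as the irRC baseline, and requires it if it is the largest. The route is narrow. Where it occurs, the main effect is a lower bar for irPR: at an assumed +20% diameter, 28% instead of 50% for the treated region, and 78% instead of 100% of the treated region at patient level with half the burden treated. In the McNemar comparison any bias from swelling that resolves favours R848.

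Two stronger readings are tempting, and the documents do not support either. One is that resolving oedema would by itself be counted as patient-level response. With half the burden treated that needs about +73% in diameter, which nothing in the plan suggests. The other is that the trial's main result is compromised. The Part 1 primary endpoint is the change in CD8+ tetramer-positive cells, and the Part 2 primary outcomes are immune-cell infiltration; neither uses this baseline. What is affected is the response endpoint, which is primary for the Arm C patients, and the secondary lesion comparison.

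The figures assume equal proportional swelling of both diameters and, at patient level, half the burden treated with untreated lesions unchanged.

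**What to change.** In section 9.6, for response scoring only (whole-patient and by lesion type):

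- Define the irRC baseline as the largest measurement up to and including the last one before R848 is first applied to the tumours. The reading taken at region assignment under section 6.0 serves as that last measurement for cutaneous lesions.
- For index lesions with no pre-gel week-8 scan, use the most recent pre-gel value, or the late week-8 scan if that lesion itself received no gel.
- Report the 10-week-maximum version as a sensitivity analysis.

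The cost is a few sentences and no new procedures. The 30 patients, the implied rule of at least 5/30 (alpha 1.56%) and the 82.1% power are unchanged. The small downside is that some non-cutaneous lesions may carry an older baseline value.

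Separately, sections 6.0, 9.6 and 10.1 give 8-week and 10-week progression allowances, and the sponsor must reconcile them. That concerns continuation of patients, and this point takes no position on it; the response baseline can be corrected independently.
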